3.2. Comparison Group

A comparison group of similar families who receive standard nutrition, exercise, and weight-related lifestyle counseling during their regularly scheduled check-ups at HWNV will serve as the comparison group for this program. Both groups of children and guardians will receive standard in-office counseling, but the intervention group will also receive the x-IHPC intervention. Standard in-office counseling includes standard counseling related to diet, exercise, and screen behaviors,. The comparison group will also get food boxes.

3.3. Randomization

None

3.4. Endpoints/Outcomes Measurements

3.4.1. Primary outcomes.

3.4.2.

Primary outcomes measured via a survey, which will include food frequency questionnaires, screen time estimates, physical activity questionnaires, estimated screen time reports, and guardian self-efficacy and confidence questions related to modifiable lifestyle behaviors.^{15 16 17} Survey data will be collected during phone calls from the PI or CHW at the outset of the study and then again at the conclusion of the study. An example survey has been included (Appendix C: Survey). The survey questions may be altered or deleted based on feedback from the study advisory board or the CHWs, as this study is based on community engagement and feedback. The final survey instrument will be submitted to this IRB for approval before the data collection begins.

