The x-IHPC will include 4 extra modules, (= 4 additional weeks of programming) that will be developed by a dietitian curriculum specialist. The expanded IHPC will also include programming just for parents to increase their involvement. A key pillar of this study is identifying and training CHWs from HWNV to be Spanish-language facilitators of x-IHPC. Training these CHWs and including them in designing the x-IHPC curriculum will ensure that the programming is culturally appropriate; includes local features that relate directly to the community's needs; and enables facilitators to respond effectively to the questions and learning needs of the parents and children involved in the program.

IHPC provides produce boxes, nutrition and meal-preparation, education, and supportive counseling to address barriers related to obtaining produce and food. The intervention provides participants with a bi-weekly produce box for 12 weeks (6 boxes total) and helps families identify sustainable ways to obtain vegetables once the produce boxes end. Providing produce boxes exposes families to new, unfamiliar vegetables that are not common in their home countries, and allows families to experiment with new recipes on a limited income. The CHW will support families by coaching them on how to prepare these unfamiliar vegetables, give tips on finding sales at grocery stores, as well as by navigation to food assistance sites including food pantries, school meal sites and bus routes, and neighborhood food distributions. Parents will learn strategies to increase vegetable consumption by addressing perceived

barriers – such as the child doesn't like vegetables. Curriculum will also include topics such as how to increase physical activity and reduce screen time. Both the families in the x-HPC and families who receive the in-office counseling will be offered the 6 vegetable food boxes, delivered on a bi-weekly basis during their time in the study.

Families will decide if they have the capacity to participate in the x-HPC intervention. They will be offered both groups, but can choose which group works for their family. We realize that this introduces selection bias into the study (families who self select to be part of the intervention are families who are interested in health and have the time and ability to attend). However, the intervention takes a lot of time and families need to choose the arm that works for their schedule.

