4.3. Data Storage

4.3.1. Data Management

Information about study subjects will be kept confidential and managed according to the requirements of the Health Insurance Portability and Accountability Act of 1996 (HIPAA). Privacy and confidentiality of all enrolled participants will be maintained.

The PI and co-PI at HWNV will have an electronic list of participants who are part of the study so they can provide the standard in-office counseling and data collection. The list will be accessed only by them on a password-protected document that is stored on password-protected computers at HWNV.

Survey data collected during the study will be uploaded directly into a secure online platform, RedCap, by the CHW collecting the data. Only the study PIs will have access to this platform to manage data.

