5.4. Confidentiality

Every effort will take place to maintain the confidentiality of the study participants. Participants will be known to the physician study PI who is providing care during in-office clinic visits. Beside the PI and the co-PI at HWNV, no other HWNV staff member will have knowledge that the participant is part of the study. The PI and co-PI at HWNV will have an electronic list of participants who are part of the study, so they can provide the standard in-office counseling and data collection. The list will be accessed only by them on a password-protected document that is stored on password-protected computers at HWNV.

Survey data collected during the study will be uploaded directly into a secured online platform, RedCap, by the CHW collecting the data. Only the Inova and the HWNV PIs, will have access to this platform to manage data. Data will be de-identified before it is shared with the statistician for analysis. De-identification will occur by giving each participant a unique study ID. The document with participant names and unique study IDs will be kept on a password protected document on the Inova PI's password-protected computer.

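### The plan lets the community health workers who coach intervention families also take those families' self-reported primary outcomes by phone at follow-up, which could bias the comparison

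*Combined protocol and SAP*

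**What the plan says.** **Who collects the primary outcomes.** Section 3.4 puts diet, screen time, physical activity, and guardian self-efficacy and confidence into one guardian survey: "Survey data will be collected during phone calls from the PI or CHW", once at the start and once at the end of the study. Sections 4.3.1 and 5.4 do not mention the PI as collector. Section 4.3.1 has survey data "uploaded directly into a secure online platform, RedCap, by the CHW collecting the data", and section 5.4 says nearly the same. CHW collection therefore looks like the expected route.

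**What else the CHWs do.** Section 3.1 states: "A key pillar of this study is identifying and training CHWs from HWNV to be Spanish-language facilitators of x-IHPC". They also help design the curriculum, and "The CHW will support families by coaching them on how to prepare these unfamiliar vegetables". The comparison group (section 3.2) receives in-office counseling and food boxes; no CHW sessions are described for it.

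**What the plan says about the call.** Appendix C gives one script, with no arm-specific version. It reassures guardians that no answer is wrong and that they are not being judged, and it opens with an Administered By line. No section says which CHW calls which family, masks the caller to arm, or requires the same type of caller in both arms.

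**What is outside the problem.** BMI, the secondary outcome, is measured by a medical assistant or the physician (section 3.4.3).

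**The concern.** The survey asks about the things the program teaches. Appendix C includes items on confidence in raising the child's vegetable intake, obtaining produce and cooking healthy meals. A guardian who has spent 12 weeks with a facilitator may give that person more favorable answers than they would give a stranger. At the baseline call this relationship does not yet exist. At follow-up it exists in the intervention arm only. Any extra favorable reporting would therefore enter as a between-group difference in change, which is the quantity the GEE analysis in section 4.2 estimates, and it would probably favor x-IHPC. Adjusting for baseline would not remove it.

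This is separate from the self-selection that sections 2.6 and 3.1 acknowledge. Self-selection concerns who is in each arm; this concerns how their answers are obtained, and the protocol does not discuss it.

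**Working it through.** **Step 1: can a coach be the caller?**

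| Question | Where | Answer |
|---|---|---|
| Who may make the survey call? | 3.4 | PI or CHW |
| Who uploads the survey data? | 4.3.1, 5.4 | The CHW who collected them |
| Who facilitates x-IHPC and coaches families? | Abstract, 3.1 | CHWs |
| Do comparison families have a facilitator? | 3.2 | None described |
| Is a facilitator barred from calling their own families? | 3.4, 4.2, Appendix C | No such rule |

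The plan permits coach-as-caller in the intervention arm, does not require it, and gives it no counterpart in the comparison arm.

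**Step 2: could adjustment remove it?** The interviewer can be identified from the Administered By line, although section 4.2 makes no use of it. Let C = 1 if the follow-up caller is the family's own facilitator. In the comparison arm C is always 0. If every intervention family is called by its coach, C equals the arm indicator and the two effects cannot be separated. If only some are, the effect of C can be estimated only from differences among the 25 intervention families. Nothing in the plan says how callers would be assigned among those families, and the number is small. A caller-adjusted model is therefore not a dependable remedy.

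**Step 3: how large could the effect be?** The plan states no effect size, SD or power, so it has no figure to reproduce. The following is an illustration.

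Inputs: n = 25 per arm (section 4.1); two-sided 0.05 (section 4.2); b, the average extra reporting shift in the intervention arm in SD units, is **assumed**. Simplifications: one outcome, a two-sample t-test in place of the GEE, no true effect, no dropout, arms otherwise comparable.

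Degrees of freedom = 2 × 25 − 2 = 48; critical value = 2.011; noncentrality = b × √(25/2) = 3.536 × b. The chance of p<0.05 is P(|T| > 2.011), with T noncentral t on 48 df.

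| Assumed b (SD) | Noncentrality | Chance of p<0.05 |
|---|---|---|
| 0 | 0 | 5% |
| 0.1 | 0.354 | 6.4% |
| 0.2 | 0.707 | 10.7% |
| 0.3 | 1.061 | 18.0% |
| 0.4 | 1.414 | 28.3% |

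A normal approximation gives 10.9%, 18.6% and 29.3% for the last three rows.

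**Step 4: partial exposure.** b is an average over the arm. If each family called by its coach shifts by s and a fraction f are so called, b = f × s. With f = 0.5 and s = 0.2 to 0.4 SD, b = 0.1 to 0.2 SD, and the chance is 6.4% to 10.7%.

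**The case against.** The strongest reply is that the plan neither requires nor hides this arrangement.

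- **The wording is permissive.** A PI may make the calls, and nothing says that any family will be called by its own coach. This stands: the point is a risk the plan leaves open.
- **The caller is recorded.** A reader might infer that the interviewer will be unknown at analysis. Appendix C contradicts that. Step 2 shows why having the name is still not enough.
- **Desirability bias is not confined to one arm.** A reader might infer that comparison guardians report to someone neutral. On the PI route that need not be so: the HWNV physician PI sees participants in clinic (section 5.4), and both arms receive in-office counseling on diet, exercise and screen behaviors (section 3.2). This stands. Only the excess attached to a coach-caller differs between arms.
- **There is a neutral script.** It is a real safeguard, and no arm-specific version is described. It does not change who is asking, so its protection is partial.
- **Section 5.4 might be read as masking.** It limits knowledge of participation among HWNV staff to the PI and co-PI. The same section has the CHW collecting the data, and section 3.1 has CHWs from HWNV running the sessions, so it cannot be relied on to mask callers. Those statements need reconciling.
- **The illustration is simplified.** The shift has no source in the documents, the test is not the planned GEE, and self-selection means the 5% starting point is itself idealized. All of this stands, so the table shows sensitivity and is not a forecast.

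**Conclusion.** The concern holds as an uncontrolled risk of differential reporting in the primary outcomes. As written, the plan allows intervention guardians, and only them, to give follow-up answers to their own coach, and the planned analysis cannot undo the consequence. BMI is not affected.

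A reader might go further and conclude that the comparison is biased, or that the false-positive rate will reach 28%. The documents support neither. They do not say how many families would be called by their facilitator, and they give no basis for the size of the shift. Under the stated assumptions the chance of a spurious p<0.05 on one outcome runs from 5% with no shift to 28.3% at an average of 0.4 SD. The upper figure requires the whole arm to average that shift.

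The change is worth making because it is cheap and acts before the data are collected, which is the only dependable point at which to act.

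**What to change.** Add to section 3.4:

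1. No CHW makes a post-baseline survey call to a family whose sessions they facilitated.
2. That call goes to a CHW who did not teach the family or, failing that, to a PI. The Inova PI is preferable, since the HWNV physician PI counsels families.
3. The same type of caller and the existing Appendix C script are used in both arms.

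Add to section 4.2: carry the Administered By field into the analysis dataset and report caller by arm descriptively. Do not rely on a caller-adjusted model. Align sections 4.3.1 and 5.4 with the rule, since they name only the CHW as collector.

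**Cost.** Appendix C puts the interview at about 15 minutes, so one follow-up round for 50 families is 50 × 15 = 750 minutes, or 12.5 hours, shared among people section 3.4 already authorizes. The price is scheduling effort. The documents do not give the number of CHWs. If there are few, more calls fall to a PI, possibly with the trained interpreter already used for consent, so it cannot be promised that no extra resource is needed.

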3.4.3. Secondary outcomes

BMI percentile of children and guardians enrolled in the study. This will be measured at each office visit by a trained medical assistant or the physician.

3.5. Consent/Accent

Once a guardian has been screened as eligible for inclusion in the study, they will be approached by the physician PI and asked if they are interested in being part of the study. If they are interested, the PI will discuss whether they are interested in joining the comparison group or the intervention group. A member of the study team will meet with the family virtually or in person and consent the guardian to be part of the study (Appendix D: Consent). This consent process will take place with a trained interpreter. The consent will be provided in both English and Spanish. The consent will be emailed to program participants prior to the

¹⁵ Bryant, M. J., Ward, D. S., Hales, D., Vaughn, A., Tabak, R. G., & Stevens, J. (2008). Reliability and validity of the Healthy Home Survey: a tool to measure factors within homes hypothesized to relate to overweight in children. *The international journal of behavioral nutrition and physical activity*, 5, 23. <https://doi.org/10.1186/1479-5868-5-23>

¹⁶ Schrempf, S., van Jaarsveld, C. H., Fisher, A., & Wardle, J. (2015). The Obesogenic Quality of the Home Environment: Associations with Diet, Physical Activity, TV Viewing, and BMI in Preschool Children. *PloS one*, 10(8), e0134490. <https://doi.org/10.1371/journal.pone.0134490>

¹⁷ Kininmonth, A. R., Schrempf, S., Smith, A., Dye, L., Lawton, C., Fisher, A., Llewellyn, C., & Fildes, A. (2021). The Home Environment Interview and associations with energy balance behaviours and body weight in school-aged children - a feasibility, reliability, and validity study. *The international journal of behavioral nutrition and physical activity*, 18(1), 167. <https://doi.org/10.1186/s12966-021-01235-3>

consent conversation when possible. Whether consent occurs virtually or in person, a hard copy of the consent will be printed and stored by the Inova PI. A copy of the consent will be given to the guardian.

3.6. Monitoring Subjects and Criteria for Withdrawal of Subjects from the Study.

Study participants may leave the study at any time, without penalty. In some cases, the participant may be withdrawn if the HWNV physician PI determines that the study intervention is too burdensome for the participant or is adversely affecting the study participant's health. If any study participant leaves the study or is withdrawn from the study, their data will not be used in analysis.

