Study Design: In order to test the effectiveness of the x-IHPC intervention, outcomes from participants in this pilot study will be compared with outcomes from a comparison group of similar participants who receive standard nutrition counseling during their regularly scheduled check-ups. The team will enroll 25 children in the x-IHPC intervention and the same number in the comparison group (n=50). Both groups will receive standard in-office counseling, but the intervention group will also receive the x-IHPC.

Study Methodology: The comparison group receives standard, in-office counseling at visits 1, 3-months and 6-months. The intervention group receives standard in-office counseling at the same intervals, and also participates in a 12-week x-IHPC developed by a dietitian curriculum specialist. In addition, a key pillar of this study is identifying and training Community Health Workers (CHWs) to be Spanish-speaking facilitators of the x-IHPC and utilizing community engagement strategies. Training these CHWs and including them in designing the x-IHPC curriculum, will ensure that the programming is culturally appropriate; includes local features that relate directly to the community's needs; and enables study facilitators to respond effectively to the questions and learning needs of the parents and children involved in the program.

Statistical Methodology:

To examine the research question, a longitudinal analysis using generalized estimating equations (GEE) will be conducted to assess if mean differences exist on dietary measures, screen time, physical activity and guardian self-efficacy and confidence between the intervention and comparison groups while accounting for the correlation among the repeated measurements and controlling for covariates.

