2.6. Recruitment

The study employs convenience sampling. Recruitment will take place through email to families who receive care at HWNV in English and Spanish as well as posters advertising the program placed in community spaces where children and families who are clients at HWNV spend time (updated recruitment flyer, Appendix B). If guardians are interested in being part of the program, there will be a contact person listed on the advertisement who will screen for eligibility. If a family is screened as eligible to be part of the x-IHPC intervention, a member of the study team will meet with the family virtually or in person and consent the guardian to be part of the study. This consent process will take place with a trained interpreter. The consent will be emailed to program participants prior to the consent conversation when possible. Whether consent occurs virtually or in person, a hard copy of the consent will be printed and stored by the Inova PI. A copy of the consent will be given to the guardian.

Participants will also be screened for eligibility during their well-child clinic visit at HWNV by the physician study PI. If guardian meets the study inclusion criteria, the PI will introduce the study to the guardian and ask if they would like more information.

Families will decide if they have the capacity to participate in the x-HPC intervention. They will be offered both groups, but can choose which group works for their family. We realize that this introduces selection bias into the study (families who self select to be part of the intervention are families who are interested in health and have the time and ability to attend). However, the intervention takes a lot of time and families need to choose the arm that works for their schedule.

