2.7. Inclusion Criteria

Inclusion criteria include:

1. Child and Parent are clients at HealthWorks for Northern Virginia
2. Child between the ages 6-12 years
3. Child has a BMI percentage greater than 85%
4. Primary parent or guardian is > 18 years of age
5. Family identifies as Hispanic and Spanish is one of the primary languages spoken in the home
6. Children will be living with the primary guardian or parent for the duration of the program
7. Access to the internet
8. Parent or guardian is willing to commit to engaging in the 12 week program

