4.2. Method of Data Analysis

Analyses will follow the intention-to-treat principle, which categorizes participants by their treatment assignments regardless of adherence to the intervention or incomplete follow-up, and includes them in all analyses. Descriptive statistics will be calculated and reported as mean, standard deviation and 95% confidence intervals for continuous variables and frequency and percentage for categorical variables. Characteristics of study participants will be compared at baseline between the intervention and control groups and tested for significance using the two-sample t-test for continuous variables and the Chi-square test for categorical variables. Comparisons that are significant at the $P<0.10$ level will be considered for inclusion in multivariable models for primary and secondary analyses given that participants will not be randomized to their respective treatment groups.

Primary analyses will examine diet quality, screen time, physical activity, and guardian self-efficacy and confidence of those in the intervention and control groups while controlling for the correlated nature of the repeated measures within participants (i.e. baseline, post-intervention, and 6-month post-intervention). Secondary analyses will compare the BMI of guardians and BMI percentile of children at the three time points between the intervention and control groups. A longitudinal data analysis strategy will be employed with generalized estimating equations with robust CIs for both primary and secondary outcomes (Albert, 1999; Ma et al., 2012). A 2-sided p-value <0.05 will be accepted to indicate statistical significance. Additional analyses will be conducted to determine if results were influenced by other covariates including demographics (age, gender, educational attainment of guardian, income, etc.). All analyses will be conducted in SAS version 9.2.

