5. HUMAN SUBJECTS PROTECTION (RISKS, BENEFITS, AND ALTERNATIVES)

5.1. Risks

This study poses minimal physical or psychological risk to the study participants. There is a risk that guardians will find the intervention time-consuming. If the burden of the intervention becomes too great, the participant can leave the study with no consequences.

Any adverse events related to the research study will be reported immediately to the IRB. Reportable events include any physical or psychological harm to any human that is related to the study intervention. Protocol deviations will also be reported to the IRB, including anything related to the study participants' safety, rights, or integrity of the study data.

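### Sections 3.6 and 4.2 give opposite rules for the data of a participant who leaves or is withdrawn after giving data, and nothing says which governs

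*Combined protocol and SAP*

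**What the plan says.** **Rule on leavers (protocol section 3.6).** Participants may leave at any time. In addition, "the participant may be withdrawn if the HWNV physician PI determines that the study intervention is too burdensome for the participant", or if it is harming the participant's health. The section then states: "If any study participant leaves the study or is withdrawn from the study, their data will not be used in analysis". It does not limit this to data after exit, or to cases where consent to data use is withdrawn.

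**Analysis principle (section 4.2).** Intention-to-treat is adopted and defined as keeping participants in their group "regardless of adherence to the intervention or incomplete follow-up, and includes them in all analyses". The method is GEE with robust confidence intervals. No working correlation and no handling of missing data are given.

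**When data are collected.** Section 3.4 has surveys at the start and the end of the study; section 4.2 speaks of three time points. BMI, a secondary outcome, is taken at each office visit. The Abstract says: "The comparison group receives standard, in-office counseling at visits 1, 3-months and 6-months", and the intervention group is seen at the same intervals.

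**Who may exit, and who decides.** Section 5.1 foresees exits for burden: "If the burden of the intervention becomes too great, the participant can leave the study with no consequences". At consent (section 3.5), "the PI will discuss whether they are interested in joining the comparison group or the intervention group". Section 2.6 says that "families need to choose the arm that works for their schedule", and an inclusion criterion in 2.7 is: "Parent or guardian is willing to commit to engaging in the 12 week program". Enrolment is 25 children per group, with no allowance for dropout.

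**The concern.** A participant who gives a baseline and then leaves has incomplete follow-up. Section 4.2 keeps that participant and section 3.6 removes all of that participant's data. The set of children in the primary comparison therefore depends on which section the analyst follows, and as written that choice could be made after exits and results are known.

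Two features make this more than a drafting slip. Section 3.6 discards values already measured, not only values that were never obtained. It also lets decisions taken after enrolment settle who is analysed, including withdrawal by a physician PI who may know the chosen group. The named grounds concern the study intervention, so exits could fall mainly in x-IHPC. That would add a second selection to the self-selection the plan already admits.

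**Working it through.** **1. The two rules side by side**

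- *Exits before giving any data:* there is nothing to analyse under either rule. They differ only in who is counted.
- *Skips sessions but stays enrolled:* kept under both rules.
- *Exits, or is withdrawn, after giving data:* kept by 4.2, removed by 3.6. This is the conflict.
- *Can no longer be reached:* 4.2 keeps the participant. Section 3.6 does not say whether this counts as leaving.

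**2. Counts**

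Inputs: 25 + 25 = 50 children (sections 2.4 and 4.1), and three visits, reading the Abstract's visit 1 as entry. I count children because no section limits enrolment to one child per family. With k exits after some data have been given, 3.6 removes all k from the analysis and 4.2 removes none.

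Planned child BMI values: 50 × 3 = 150. Suppose 5 children exit after the 3-month visit:

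- Section 3.6 deletes 5 × 2 = 10 measured values, and the 5 six-month values are also absent. This leaves 150 − 15 = 135.
- Under 4.2 only the 5 six-month values are missing, which leaves 145.

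For surveys, a leaver under 3.6 loses the baseline only if there are two surveys (section 3.4), or up to two completed surveys if there are three (section 4.2).

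**3. Is 3.6 always the more biased rule for the surveys?**

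The documents give no exit rates, so this is illustration under assumptions: no true effect; two surveys with equal variance and correlation r; a fraction p of x-IHPC exits and nobody in the comparison group; leavers' follow-up is missing; leavers are g SD less favourable than stayers on whatever drives exit. Bias in the between-group difference in mean change, in SD, is p × g times the factor below. Positive values favour x-IHPC.

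| Exit depends on | Leavers excluded (3.6) | Baselines kept, independence GEE | Baselines kept, exchangeable GEE |
|---|---|---|---|
| follow-up value | 1 − r | 1 | 1 − r² |
| change | √(2(1 − r)) | √((1 − r)/2) | (1 + r)√((1 − r)/2) |
| baseline value | −(1 − r) | r | 0 |

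With p = 5/25 = 0.2, g = 0.5 and r = 0.5, p × g = 0.10. The rows become 0.05 / 0.10 / 0.075, then 0.10 / 0.05 / 0.075, then −0.05 / 0.05 / 0.

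Over g = 0.5 to 0.9 and r = 0.3 to 0.7, exclusion gives:

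- 0.03 to 0.13 when exit depends on the follow-up value;
- 0.08 to 0.21 when it depends on change;
- −0.13 to −0.03 when it depends on baseline.

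Keeping baselines gives, for independence and exchangeable GEE respectively:

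- 0.10 to 0.18 and 0.05 to 0.16 (follow-up value);
- 0.04 to 0.11 and 0.07 to 0.14 (change);
- 0.03 to 0.13 and about 0 (baseline).

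Exclusion is thus the less biased rule in the first row and the more biased in the second. In the third row its sign is reversed. All entries scale with p: a single exit (1/25 = 0.04) gives one fifth of each figure. Equal exits by the same mechanism in both groups would cancel.

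**4. The part due to 3.6 alone**

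For the 3-month BMI comparison, a child who exits after that visit has both values. Section 4.2 then adds no exit bias, and 3.6 adds the first-column factor. With p = 0.2, g = 0.5 to 0.9 and r = 0.3 to 0.9, this is 0.01 to 0.13 (exit depends on the 3-month level), 0.04 to 0.21 (change) or −0.13 to −0.01 (baseline). At r = 0.9 the ranges shrink to about 0.01 to 0.02, 0.04 to 0.08 and −0.02 to −0.01. It concerns a secondary outcome, and does not arise for exits before the 3-month visit.

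**The case against.** The strongest reply is that this is a small, self-selected pilot. Without randomisation, intention-to-treat cannot give its usual protection, and the plan is open about selection bias. Free choice of group and the 12-week commitment criterion make exits less likely, and both groups are offered the same produce boxes, which may help retention in each. This stands as a reason not to predict many exits. It does not say which rule applies when one occurs.

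Section 3.6 might also be read as protecting people who withdraw consent. Its wording does not allow that limit: it also covers participants withdrawn by the physician PI, who may be content for their data to be used.

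A reader might infer more than the documents support:

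- *That 3.6 biases the trial in favour of x-IHPC.* No exit rates or reasons are given, the sign depends on what drives exit, and for outcomes surveyed only at start and end 3.6 can be the less biased rule. Much of the illustrated bias comes from the missing follow-up itself.
- *That any exit triggers the conflict, or that 4.2 always analyses 50.* The exit must come after some data exist.
- *That imputation is needed to resolve it.* One stated rule for data collected before exit is enough.

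**Conclusion.** The contradiction is certain and stands in the current text. From the first participant who exits after giving data, sections 3.6 and 4.2 define different analysis sets, differing by k of the 50 children, and the documents do not rank them. The loss of 10 measured child BMI values for 5 exits after month 3 rests only on reading the visits as entry, 3 and 6 months.

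Post-enrolment selection is plausible, because burden is a named ground for exit and the person who may withdraw participants may know their group. Its size and direction cannot be stated; the figures in the working are illustrations and carry no weight in this conclusion. The point must be settled before analysis because the analysis set is undefined, not because a particular bias has been shown.

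**What to change.** Subject to the consent form, which is not in the copy reviewed:

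1. Replace the data sentence in 3.6 with: *Data collected up to exit are kept and analysed in the group chosen at enrolment; data are excluded only where consent to data use is withdrawn.*
2. State in 4.2 that this set is the primary analysis, with group meaning the group chosen at enrolment, since nobody is assigned.
3. Show the analysis that excludes leavers only as a sensitivity analysis.
4. Report exits by group, time and reason.

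Where the consent form allows, those who leave may be asked for the closing survey and may decline without penalty. A named imputation method is optional.

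The cost is edits to two sections, an IRB amendment, alignment of the consent form (with data from those already enrolled handled as their consent allows), and a few calls. The withdrawal criteria themselves are not at issue.
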